4.2. Exclusion Criteria

Subjects who meet any of the following criteria will be disqualified from entering the study:

1. Medical history of myocardial infarction within 6 months before randomization/registration, symptomatic congestive heart failure (CHF) (New York

Heart Association Class II to IV, Section 17.4), troponin levels consistent with myocardial infarction as defined according to the manufacturer, unstable angina, or serious cardiac arrhythmia requiring treatment within 28 days before randomization/registration

2. Has a corrected QT interval (QTc) prolongation to > 470 msec (females) or >450 msec (males) based on average of the screening triplicate 12-lead ECG
3. Has a history of (non-infectious) ILD/pneumonitis that required steroids, has current ILD/pneumonitis, or where suspected ILD/pneumonitis cannot be ruled out by imaging at screening
4. Brain metastases that are untreated, symptomatic, or require therapy to control symptoms, as well as any history of radiation, surgery, or other therapy, including steroids or anticonvulsants, to control symptoms from brain metastases within 2 months (60 days) of randomization/registration. After approximately 30 subjects with inactive brain metastases [20% of the 150 planned to receive the RP2D] have been enrolled at the RP2D, subsequent subjects with any current or past history of brain metastases will be excluded
5. Has clinically significant corneal disease in the opinion of the investigator
6. History of severe hypersensitivity reactions to other monoclonal antibodies
7. Substance abuse or medical conditions such as clinically significant cardiac or pulmonary diseases or psychological conditions, that may, in the opinion of the investigator, interfere with the subject's participation in the clinical study or evaluation of the clinical study results
8. Social, familial, or geographical factors that would interfere with study participation or follow-up
9. Uncontrolled infection requiring IV antibiotics, antivirals, or antifungals
10. Known human immunodeficiency virus (HIV) infection, or active hepatitis B surface antigen or C infection. Subjects should be tested for HIV prior to randomization if required by local regulations or institutional review board (IRB)/ethics committee (EC)
11. History of other malignancy(ies), except adequately treated non-melanoma skin cancer, curatively treated in-situ disease, or other solid tumors curatively treated, with no evidence of disease for ≥ 3 years
12. Prior treatment with an ADC which consists of an exatecan derivative that is a topoisomerase I inhibitor.
13. Unresolved toxicities from previous anticancer therapy, defined as toxicities (other than alopecia) not yet resolved to grade ≤ 1 or baseline. Subjects with chronic Grade 2 toxicities may be eligible per the discretion of the investigator after consultation with the Sponsor Global Clinical Lead or designee (eg, Grade 2 chemotherapy-induced neuropathy)
14. Therapeutic radiation therapy or major surgery within 4 weeks before study drug treatment or palliative radiation therapy within 2 weeks before study drug treatment

15. Systemic treatment with anticancer therapy, antibody-based therapy, retinoid therapy, or hormonal therapy within 3 weeks before study drug treatment; or treatment with nitrosoureas or mitomycin C within 6 weeks before study drug treatment; or treatment with small-molecule targeted agents within 2 weeks, or 5 half-lives before study drug treatment, whichever is longer
16. Current treatment with CYP3A4 strong inhibitors and OATP1B inhibitors (Section 17.5) (washout period of ≥ 3 elimination half-lives of the inhibitor is required)
17. Participation in a therapeutic clinical study within 3 weeks before study drug treatment (for small-molecule targeted agents [eg, inhibitors], this non-participation period is 2 weeks or 5 half-lives, whichever is longer), or current participation in other investigational procedures
18. Pregnant or breastfeeding, or planning to become pregnant
19. Subject must not be a family member of study site personnel or of Sponsor personnel.
20. Has a history of severe hypersensitivity reactions to either the drug substances or inactive ingredients in the drug product.

5. STUDY TREATMENT(S)

5.1. Assigning Subjects to Treatments

5.1.1. Treatment Group(s)

There will be subjects randomized to 3 different treatment groups: 5.4 mg/kg, 6.4 mg/kg, and 7.4 mg/kg Q3W in the PK stage and two treatment groups in the dose finding stage. Once assigned, subjects will remain on study in their treatment group and will not change dose groups. There will be 1 treatment group in Part 2 of this study (at the RP2D of 5.4 mg/kg).

5.1.2. Method of Treatment Allocation

For the PK Stage of Part 1, eligible subjects will be randomized by the interactive web/voice response system (IXRS) in a 1:1:1 ratio into 1 of 3 treatment groups: 5.4 mg/kg, 6.4 mg/kg, and 7.4 mg/kg.

For the Dose Finding Stage of Part 1, eligible subjects will be randomized by the IXRS in a 1:1 ratio into 1 of 2 treatment groups selected after the PK Stage.

Randomization will be stratified by region (Asia, rest of world).

For Part 2, eligible subjects will not be randomized, but will instead be registered in IXRS.

5.1.3. Blinding

This study is an open-label study and no blinding will be performed.

5.2. Study Drug(s)

5.2.1. Description

Two dosage forms of DS-8201a drug product will be supplied.

The DS-8201a drug product containing 100 mg of DS-8201a is either provided as:

[REDACTED]-DP2)

The DS-8201a drug product **[REDACTED]**

[REDACTED] Each vial is designed for single use only and is not to be used to treat more than one subject.

or

[REDACTED]-DP)

The DS-8201a drug product **[REDACTED]**

[REDACTED] Each vial is designed for single use only and is not to be used to treat more than one subject. **[REDACTED]**

5.2.2. Labeling and Packaging

DS-8201a will be supplied by the Sponsor. DS-8201a Injection study drug will be clinical-labeled in compliance with regulatory requirements and packaged. The packaging will clearly display the name of the investigational product, the investigational product manufacturing code, storage condition and other required information in accordance with local regulations.

5.2.3. Preparation

The drug for IV infusion is prepared by dilution of the required volume of the drug product calculated based on the subject's body weight in a volume of 100 mL. Prepared medicinal solutions should be used immediately. The preparation will be conducted in accordance with the Pharmacy Manual provided by the Sponsor. Procedures for proper handling and disposal of anticancer drugs should be followed in compliance with the standard operating procedures (SOPs) of the study site. Refer to the Pharmacy Manual for detailed information about preparation and administration of DS-8201a.

5.2.4. Administration

The investigational drug will be administered initially as a 7.4 mg/kg, 6.4 mg/kg, or 5.4 mg/kg IV every 3 weeks. The initial dose of DS-8201a will be infused for 90 ± 10 minutes. If there is no infusion-related reaction, after the initial dose, the next dose of DS-8201a will be infused for 30 ± 5 minutes. The subject's weight at screening (baseline) will be used to calculate the initial dose. If during the course of treatment the subject's weight changes by $\pm 10\%$ of the baseline weight, the subject's dose will be recalculated based on the subject's updated weight. Two drug materials will be used in this study. [REDACTED]

[REDACTED] The transition from [REDACTED] to [REDACTED] is expected to occur at approximately the start of Part 2 of the trial.

5.2.5. Storage

Drug supplies must be stored in a secure, limited access storage area under the storage conditions listed below:

- Stored [REDACTED]
- Stored [REDACTED]

If storage conditions are not maintained per specified requirements, Sponsor or contract research organization (CRO) should be contacted.

5.2.6. Drug Accountability

When a drug shipment is received, the investigator or designee will check the amount and condition of the drug, check for appropriate local language in the label, drug expiration date, and sign the Receipt of Shipment Form provided. The Receipt of Shipment Form should be signed and the original form will be retained at the site. In addition, the investigator or designee shall contact Sponsor as soon as possible if there is a problem with the shipment.

A Drug Accountability Record will be provided for the investigational product. The record must be kept current and should contain the following:

- dates and quantities of drug received,
- subject's identification number and/or initials or supply number (as applicable),
- the date and quantity of investigational product dispensed and remaining (if from individual subject drug units),
- the initials of the dispenser.

At the end of the study, as per local laws and/or directed by Sponsor, all unused DS-8201a will be returned or destroyed as per local laws or site policy and only after the study monitor has completed a final inventory. As applicable, the study site must file a copy of the appropriate institution policy within their investigator site file and provide a copy to the Sponsor. Please see Pharmacy Manual for details.

All investigational product inventory forms must be made available for inspection by a Sponsor authorized representative or designee and regulatory agency inspectors.

5.3. Control Treatment

Not applicable.

5.4. Dose Interruptions and Reductions

The investigator will evaluate which toxicities are attributed to the study drug and adjust the dose of the drug as recommended below. All dose modifications should be based on the worst preceding toxicity (common toxicology criteria [CTC]AE version 4.03). Specific criteria for interruption, re-initiation, dose reduction and/or discontinuation of DS-8201a are listed in [Table 5.2](#). All interruptions or modifications must be recorded on the AE and drug administration case report form (CRF). Appropriate clinical experts should be consulted as deemed necessary.

For Grade 3 or Grade 4 events, monitoring (including local laboratory tests when appropriate) should be performed at intervals no greater than 7 days until AE is determined to be resolving or subject is discontinued at end of treatment.

Prophylactic or supportive treatment for expected toxicities, including management of study-drug induced AEs will be as per treating physician discretion and institutional guidelines.

Dose Reduction Guidelines:

NOTE: There will be no dose modifications for Grade 1 or Grade 2 AEs unless specified below in [Table 5.2](#).

Two dose reductions will be permitted. The adjustment for reduced dosing of DS-8201a is as shown in [Table 5.1](#).

Table 5.1: Dose Reduction Levels of DS-8201a

Starting Dose	Dose Level -1	Dose Level -2
7.4 mg/kg	6.4 mg/kg	5.4 mg/kg
6.4 mg/kg	5.4 mg/kg	4.4 mg/kg
5.4 mg/kg	4.4 mg/kg	3.2 mg/kg

Once the dose of DS-8201a has been reduced because of toxicity, all subsequent cycles should be administered at that lower dose level unless further dose reduction is required. More than 2 dose reductions are not allowed and the subject will be withdrawn from the study treatment if further toxicity meeting the requirement for dose reduction occurs. DS-8201a dose increases are not allowed in the study.

Dose can be interrupted for up to 28 days from the planned date of administration. If a subject is assessed as requiring a dose delay longer than 28 days, the subject will be withdrawn from the study.

Treatment cycles for a subject for whom DS-8201a dosing was temporarily withheld for any reason may have future cycles scheduled based on the date of the last DS-8201a dose.

Investigators may contact the Sponsor’s Global Clinical Lead or designee to discuss questions regarding dose modification or discontinuation of study drug.

Table 5.2: Dose modification for DS-8201a

Worst toxicity CTCAE v4.03 Grade (unless otherwise specified)	Dose or schedule modification for DS-8201a
No toxicity	Maintain dose and schedule
Infusion Reaction	
Grade 1 (Mild transient reaction; infusion interruption not indicated; intervention not indicated)	If infusion-related reaction (such as fever and chills, with and without nausea/vomiting, pain, headache, dizziness, dyspnea, hypotension) is observed during administration, the infusion rate should be reduced by 50% and subjects should be closely monitored. If no other reactions appear, the subsequent infusion rate could be resumed at the initial planned rate.
Grade 2 (Therapy or infusion interruption indicated but responds promptly to symptomatic treatment (eg, antihistamines, nonsteroidal anti-inflammatory drugs (NSAIDs), narcotics, IV fluids); prophylactic medications indicated for ≤24 h)	Administration of DS-8201a should be interrupted and symptomatic treatment started (eg, antihistamines, NSAIDs, narcotics, intravenous fluids). If the event resolves or improves to grade 1, infusion can be re-started at a 50% reduced infusion rate. Subsequent administrations should be conducted at the reduced rate.
Grade 3 or 4 (Prolonged or life-threatening consequences, urgent intervention indicated)	Administration of DS-8201a should be discontinued immediately and permanently. Urgent intervention indicated. Antihistamines, steroids, epinephrine, bronchodilators, vasopressors, intravenous fluid therapy, oxygen inhalation etc., should be administered.

Table 5.2: Dose modification for DS-8201a (Continued)

Worst toxicity CTCAE v4.03 Grade (unless otherwise specified)	Dose or schedule modification for DS-8201a
Hematologic Toxicity	
Neutrophil Count Decreased and/or White Blood Cell Count Decreased	
Grade 3	Delay dose until resolved to \leq Grade 2, then maintain dose
Grade 4	Delay dose until resolved to \leq Grade 2, Reduce dose 1 level
Febrile Neutropenia (absolute neutrophil count $< 1 \times 10^9/L$, fever $> 38.3^\circ C$ or a sustained temperature of $\geq 38^\circ C$ for more than one hour)	Delay dose until resolved, Reduce dose by 1 level
Lymphocyte Count Decreased	
Grade 1 to Grade 3 lymphopenia	No dose modification
Grade 4 ($< 0.2 \times 10^9/L$)	Delay dose until resolved to \leq Grade 2: 
 • If resolved in ≤ 14 days, maintain dose • If resolved in > 14 days, reduce dose 1 level
Anemia	
Grade 3 (Hemoglobin (Hg) < 8.0 g/dL); transfusion indicated	Transfuse. Delay dose until resolved to \leq Grade 2, then maintain dose
Grade 4 (Hg < 8.0 g/dL) Life threatening consequences; urgent intervention indicated	Transfuse. Delay dose until resolved to \leq Grade 2, then reduce dose 1 level
Platelet Count Decreased	
Grade 3 (platelets < 50 to $25 \times 10^9/L$)	Delay dose until resolved to \leq Grade 1: 
 • If resolved in ≤ 7 days, maintain dose • If resolved in > 7 days, reduce dose 1 level
Grade 4 (platelets $< 25 \times 10^9/L$)	Delay dose until resolved to \leq Grade 1, then reduce dose 1 level
Cardiac Toxicity	
Symptomatic congestive heart failure (CHF)	Discontinue subject from study treatment
Decrease in left ventricular ejection fraction (LVEF) 10-20% (absolute value), but LVEF $> 45\%$	Continue treatment with DS-8201a
LVEF 40% to $\leq 45\%$ and decrease is $< 10\%$ (absolute value) from baseline	Continue treatment with DS-8201a Repeat LVEF assessment within 3 weeks

Table 5.2: Dose modification for DS-8201a (Continued)

Worst toxicity CTCAE v4.03 Grade (unless otherwise specified)	Dose or schedule modification for DS-8201a
LVEF 40% to \leq 45% and decrease is \geq 10% (absolute value) from baseline	Interrupt DS-8201a dosing Repeat LVEF assessment within 3 weeks. If LVEF has not recovered to within 10% from baseline, discontinue subject from study treatment
LVEF < 40% or > 20% (absolute value) drop from baseline	Interrupt DS-8201a dosing Repeat LVEF assessment within 3 weeks. If LVEF < 40% or > 20% drop from baseline is confirmed, discontinue subject from study treatment
Corrected QT (QTc) Prolongation	
Grade 3 (QTc > 500 ms on 2 separate electrocardiograms)	Delay dose until resolved to \leq Grade 1 (QTc \leq 480 ms), determine if another medication the subject was taking may be responsible and can be adjusted, then if attributed to DS-8201a, reduce dose 1 level
Grade 4 (QTc > 500 or > 60 ms change from baseline and Torsade de pointes or polymorphic ventricular tachycardia or signs/symptoms of serious arrhythmia)	Discontinue subject from study treatment
Troponin	
Grade 1 (Levels above the upper limit of normal and below the level of myocardial infarction as defined by the manufacturer)	If troponin levels are above the upper limit of normal and below the level of myocardial infarction as defined by the manufacturer (CTCAE Grade 1) at baseline, no repeat testing is required if the troponin level is not Grade 3 Repeat troponin testing at 3 ± 1 hours after initial troponin test. 
 • If repeat troponin level at 3 ± 1 hours rises significantly per institutional guidelines, 
 - perform ECG in triplicate; - repeat troponin testing at 6 ± 1 hours after initial troponin test; - follow institutional guidelines for management of detectable troponin testing. • If repeat troponin level at 3 ± 1 hours does not rise significantly per institutional guidelines, 
 - repeat troponin testing at 6 ± 1 hours or at 24 ± 2 hours after initial troponin test. Continue treatment with DS-8201a.
Grade 3 (Levels consistent with myocardial infarction as defined by the manufacturer)	Perform ECG in triplicate Repeat troponin testing at 6 hours and 12 hours after initial troponin test. Follow institutional guidelines for management of detectable troponin testing. If AMI confirmed, discontinue subject from study therapy. Delay dose until resolved to \leq Grade 1: 
 • If resolved in \leq 7 days, maintain dose • If resolved in > 7 days, reduce dose 1 level

Table 5.2: Dose modification for DS-8201a (Continued)

Worst toxicity CTCAE v4.03 Grade (unless otherwise specified)	Dose or schedule modification for DS-8201a
Pulmonary Toxicity	
If a subject develops an acute onset of new or worsening pulmonary or other related signs/symptoms such as dyspnea, cough or fever, rule out ILD/pneumonitis.
 
If the AE is confirmed to have an etiology other than ILD/pneumonitis, follow the management guidance outlined in the “Other Non-Laboratory Adverse Events” dose modification section below.
 
If the AE is suspected to be ILD/pneumonitis, treatment with study drug should be interrupted pending further evaluations.
 
Evaluations should include:
 
 • High resolution CT • Pulmonologist consultation • Pulmonary function tests and pulse oximetry (SpO₂) • Arterial blood gases if clinically indicated • One blood sample collection for PK and exploratory biomarker analysis as soon as ILD/pneumonitis is suspected, if feasible 
Other tests could be considered as needed.
 
As soon as ILD/pneumonitis is suspected, corticosteroid treatment should be started promptly as per clinical treatment guidelines (Kubo K, et al 2013 for guidance²²).
 
If the AE is confirmed to be ILD/pneumonitis, follow the management guidance as outlined below.
 
All events of ILD regardless of severity or seriousness will be followed until resolution including after drug discontinuation.

Grade 1	
The administration of DS-8201a must be interrupted for any ILD event regardless of grade.
 
For Grade 1 events, DS-8201a can be restarted only if the event is fully resolved to Grade 0:
 
 • If resolved in ≤ 28 days from day of onset, maintain dose • If resolved in > 28 days from day of onset, reduce dose 1 level
Grade 2, 3, or 4	Permanently discontinue subject from study treatment.
Ocular	
Grade 3	
Delay dose until resolved to \leq Grade 1:
 
 • If resolved in ≤ 7 days, maintain dose • If resolved in > 7 days, reduce dose 1 level
Grade 4	Discontinue subject from study treatment
Renal Toxicity (serum creatinine)	
Grade 3 (> 3 to $6 \times$ upper limit of normal [ULN])	Delay dose until resolved to \leq Grade 2 or baseline, then reduce dose 1 level
Grade 4 ($> 6 \times$ ULN)	Discontinue subject from study treatment

Table 5.2: Dose modification for DS-8201a (Continued)

Worst toxicity CTCAE v4.03 Grade (unless otherwise specified)	Dose or schedule modification for DS-8201a
Hepatic Toxicity	
Aspartate Transaminase (AST) or Alanine Transaminase (ALT) with Simultaneous Total Bilirubin (TBL) Increased	
AST/ALT $\geq 3.0 \times$ ULN with simultaneous TBL $> 2.0 \times$ ULN	
Delay study medication until drug-induced liver injury can be ruled out. If drug-induced liver injury is ruled out, the subject should be treated accordingly, and resumption of study drug may occur after discussion between the investigator and Sponsor.
 
If drug-induced liver injury cannot be ruled out from diagnostic workup, permanently discontinue study treatment.
 
Monitor AST/ALT and TBL twice weekly until resolution or return to baseline.

Aspartate Transaminase (AST) or Alanine Transaminase (ALT)	
Grade 2 ($> 3.0 - 5.0 \times$ ULN)	No action for Grade 2 AST/ALT
Grade 3: $> 5.0 - 20.0 \times$ ULN In subjects without liver metastases and subjects with liver metastases and baseline level $\leq 3 \times$ ULN:	
Repeat testing within 3 days. Delay dose until resolved to \leq Grade 1, then:
 
 • If resolved in ≤ 7 days from day of onset, maintain dose • If resolved in > 7 days from day of onset, reduce dose 1 level
Grade 3 ($> 8.0 - 20.0 \times$ ULN) In subjects with liver metastases, if the baseline level was $> 3 \times$ ULN	
Repeat testing within 3 days. Delay dose until resolved to \leq baseline level, then:
 
 • If resolved in ≤ 7 days from day of onset, maintain dose • If resolved in > 7 days from day of onset, reduce dose 1 level
Grade 4 ($> 20 \times$ ULN)	Discontinue subject from study treatment
Total Bilirubin	
Grade 2 ($> 1.5 - 3.0 \times$ ULN)	
If no documented Gilbert's syndrome or liver metastases at baseline, delay dose until resolved to \leq Grade 1:
 
 • If resolved in ≤ 7 days from day of onset, maintain dose • If resolved in > 7 days from day of onset, reduce dose 1 level 
If documented Gilbert's syndrome or liver metastases at baseline, continue study treatment

Grade 3 ($> 3.0 - 10.0 \times$ ULN)	
If no documented Gilbert's syndrome or liver metastases at baseline, repeat testing within 3 days. Delay dose until resolved to \leq Grade 1:
 
 • If resolved in ≤ 7 days from day of onset, reduce dose 1 level • If resolved in > 7 days from day of onset, discontinue DS-8201a 
If documented Gilbert's syndrome or liver metastases at baseline, repeat testing within 3 days. Delay dose until resolved to \leq Grade 2:
 
 • If resolved in ≤ 7 days from day of onset, reduce dose 1 level • If resolved in > 7 days from day of onset, discontinue DS-8201a
Grade 4 ($> 10.0 \times$ ULN)	Discontinue subject from study treatment
Alkaline Phosphatase Increased	
Grade 3 or 4 ($> 5.0 \times$ ULN)	No modification unless determined by the investigator to be clinically significant or life-threatening

Table 5.2: Dose modification for DS-8201a (Continued)

Worst toxicity CTCAE v4.03 Grade (unless otherwise specified)	Dose or schedule modification for DS-8201a
Gastrointestinal	
Nausea	
Grade 3	Delay dose until resolved to \leq Grade 1: 
 • If resolved in \leq 7 days, maintain dose • If resolved in $>$ 7 days, reduce dose 1 level
Diarrhea/Colitis	
Grade 3	Delay dose until resolved to \leq Grade 1: 
 • If resolved in \leq 3 days, maintain dose • If resolved in $>$ 3 days, reduce dose 1 level
Grade 4	Discontinue subject from study treatment
Other Laboratory Adverse Events	
Grade 3	Delay dose until resolved to \leq Grade 1 or baseline level: 
 • If resolved in \leq 7 days, maintain dose • If resolved in $>$ 7 days, reduce dose 1 level
Grade 4	Discontinue subject from study treatment
Other Non-laboratory Adverse Events	
Grade 3	Delay dose until resolved to \leq Grade 1 or baseline: 
 • If resolved in \leq 7 days, maintain dose • If resolved in $>$ 7 days, reduce dose 1 level
Grade 4	Discontinue subject from study treatment

All dose modifications should be based on the worst preceding toxicity.

CTCAE: Common Terminology Criteria for Adverse Events.

In addition, investigators may consider dose reductions or discontinuations of the study drug according to the subject's condition and after discussion with the Sponsor Global Clinical Lead or designee.

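### Table 5.2 applies a weaker LVEF test after a deeper fall (below 40%, or by more than 20 points) than after a fall to 40-45%, and gives the deeper fall no restart criterion

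*Combined protocol and SAP*

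**What the plan says.** Protocol Section 5.4 sends the reader to one table for every dosing decision: "Specific criteria for interruption, re-initiation, dose reduction and/or discontinuation of DS-8201a are listed in" Table 5.2. It adds a general rule: "All dose modifications should be based on the worst preceding toxicity".

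Three cardiac rows of Table 5.2 matter here.

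- **Continue row.** "Decrease in left ventricular ejection fraction (LVEF) 10-20% (absolute value), but LVEF" is above 45%: treatment continues.
- **Recovery row.** LVEF 40-45% and at least 10 points below baseline: interrupt, repeat within 3 weeks, then "If LVEF has not recovered to within 10% from baseline, discontinue subject from study treatment". The row sets no upper limit on the fall.
- **Severe row.** LVEF below 40%, or more than 20 points below baseline: interrupt and repeat within 3 weeks. If LVEF below 40% or a more than 20% "drop from baseline is confirmed, discontinue subject from study treatment". The row says nothing about when dosing may resume.

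Eligibility requires a baseline LVEF of at least 50% (Section 4.1, criterion 6).

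**The concern.** The recovery row asks whether the heart has recovered. The severe row asks only whether the bad reading was real. A subject with the worse event can therefore pass on a repeat value that ends treatment for a subject with the milder event.

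The severe row also lacks the re-initiation criterion that Section 5.4 says the table contains. Other interruption rows give one: QTc prolongation must resolve to Grade 1 or lower (480 ms or less), and a low platelet count must resolve to Grade 1 or lower.

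What is at stake is the safety of individual subjects. Section 9.3.2 lists cardiotoxicity among the adverse events of special interest and calls it an important potential risk.

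**Working it through.** Let B be the baseline LVEF, I the index value that caused the interruption and R the repeat, all in whole percentage points. The rules come from Table 5.2. A repeat exactly 10 points down is taken as within 10.

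- Recovery row: applies if 40 ≤ I ≤ 45 and B − I ≥ 10. Stop if B − R > 10.
- Severe row: applies if I < 40 or B − I > 20. Stop if R < 40 or B − R > 20.
- Continue row, applied to the repeat: R > 45 and 10 ≤ B − R ≤ 20.

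The two tests disagree, with nothing else stopping the subject, when R > 45 and 10 < B − R ≤ 20. A repeat of 40-45% is left out because it triggers the recovery row again.

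**Example.** B = 60, R = 48, so B − R = 12.
- I = 42: the fall is 18, so only the recovery row applies. 12 > 10, so the subject must stop.
- I = 38: the fall is 22, so only the severe row applies. 48 is not below 40 and 12 is not above 20, so there is no stop rule. R = 48 fits the continue row.

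**Where this is unambiguous.** A conflicting repeat needs R ≥ 46 and R ≤ B − 11, so B ≥ 57. The whole 40-45% band meets the recovery row alone when B − 40 ≤ 20, so B ≤ 60. At these baselines every severe-row index is 39% or lower.

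| Baseline | Conflicting repeats |
|---|---|
| 57 | 46 |
| 58 | 46-47 |
| 59 | 46-48 |
| 60 | 46-49 |

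**From 61% upward.** An index in the 40-45% band meets both rows when I < B − 20. That is 40 at B = 61, 40-44 at B = 65, and all of 40-45 from B = 66 (66 − 45 = 21). Two readings are possible.
- *The severe row alone governs.* An index under the recovery test must satisfy B − 20 ≤ I ≤ 45, so B ≤ 65. The inversion ends there. At B = 65 only an index of 45 gets the recovery test (conflicting repeats 46-54).
- *The recovery test still applies to any index of 40-45%.* The inversion then persists above 65% against an index below 40%. For example, with B = 70 and R = 58 (12 down), I = 42 must stop and I = 38 meets no stop rule.

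**Points or relative percent.** The trigger cells of both interruption rows say absolute value; their action cells do not repeat it. If both action cells are read as relative, the severe row stops some of these repeats, but not all. At B = 57, R = 46 the drop is 11/57 = 19.3%, not above 20%. At B = 60, R = 48 it is 12/60 = 20.0%, not above 20%. In both cases the recovery row still stops the subject, because the drop exceeds 10%.

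**Time to the next scan.** Section 6.4.1 schedules Echo or MUGA every 4 cycles (± 7 days). If the index scan was a scheduled one before the interrupted dose, the next scheduled scan falls 4 × 21 = 84 ± 7 days after the resumed dose. That is 11 to 13 weeks and four doses. After an unscheduled index scan it could come sooner.

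**Frequency.** The documents give no rate for this pattern. The nearest figure is ejection fraction decreased in 2 of 148 subjects in the Phase 1 study (Section 1.1.1.5): 1.4%, exact 95% CI 0.2% to 4.8%. Both were Grade 2, with no action on study drug. That interim count comes from a study that scanned every 2 cycles. It is neither a rate for this pattern nor a ceiling on it.

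**The case against.** The strongest reply is that a confirmation test suits a large drop from a high baseline when LVEF is still good. That is fair, but an index above 45% in the severe row needs B − 46 > 20, so a baseline of at least 67%. It does not cover the window above.

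A second reply is that no clinician would restart on these values without thought. Several safeguards do exist.
- Symptomatic heart failure ends treatment (Table 5.2), and troponin is measured after each infusion (Section 9.3.2.2).
- Grade 3 or 4 events are monitored "at intervals no greater than 7 days until AE is determined to be resolving".
- After discussion with the sponsor, "investigators may consider dose reductions or discontinuations of the study drug".
- Section 5.7.1 allows withdrawal for an adverse event or by physician decision. It also lets a subject who is benefiting stay on treatment after discussion, so neither outcome is absolute.
- Section 11.5.1 provides ongoing review of individual data and monthly aggregate safety review.

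All of this reduces the risk, but none of it sets an LVEF level for restarting. Nor does the limit on delay force a stop: "Dose can be interrupted for up to 28 days from the planned date of administration", while the repeat is due within 21. The Grade 3 row for other non-laboratory events does require recovery to Grade 1 or baseline, but its title most naturally excludes LVEF, which has its own rows.

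A third reply is that the recovery row may be the outlier, since the continue row accepts a fall of 10-20 points with LVEF above 45%. This stands as an argument about which threshold to choose. It does not justify a stricter threshold for the milder fall.

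**Conclusion.** The inversion is real as the table is written. It is unambiguous at baselines 57-60%, all eligible. How far it extends above 60% depends on a rule the table does not give. The conclusion rests on whole-number LVEF and on reading the limits as percentage points; under the relative reading it narrows but remains.

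Three stronger readings are not supported.
- A reader might infer that the protocol directs dosing to resume after a deep fall. It does not say so. Resumption is inferred from the absence of a stop rule and from the continue row. The firm statement is that the restart criterion is missing.
- A reader might take 57-65% as the exact window. That holds only if an index meeting both rows is judged by the severe row alone. The worst-preceding-toxicity rule does not settle this, since it could also mean that both tests apply.
- A reader might infer a material risk across the trial. The documents give no incidence, few subjects are likely to be affected, and the efficacy analysis is untouched.

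It should still be corrected, because it is a mandatory safety rule ordered the wrong way for a named risk.

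**What to change.** In the severe row of Table 5.2, keep discontinuation when the finding is confirmed, and add the following.

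1. When the index LVEF was 45% or lower, dosing may resume only if the repeat is within 10 points of baseline; otherwise discontinue.
2. This also governs an index that meets both interruption rows.
3. The continue row does not govern the repeat after such an interruption.

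Leave the confirmation test as it is for a drop of more than 20 points with the index still above 45%. For example, baseline 70%, index 49%, repeat 59% is not discontinued, as now. If the sponsor's cardiac experts prefer another recovery threshold, apply it to every index of 45% or lower that led to interruption. Either way, a deeper fall is never handled more leniently.

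The cost is one table row and a clarifying sentence in the next amendment. No procedure is added, because both rows already require the repeat within 3 weeks. The downside is that a few subjects with a deep, partly recovered fall would stop treatment. Some would have high baselines: baseline 70%, index 38%, repeat 58% would now stop. Section 1.2 describes the remaining chemotherapy as only marginally effective, so the sponsor should choose the threshold with that loss in view.
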